#### Per-protocol Analysis Set

The per-protocol analysis set will be of participants followed according to the schedule outlined. For the primary analysis, which is based on 60 days, the per-protocol adherence is only during the first 60 days. The results of this potentially non-representative subset(s) will be compared to the results obtained using the ITT Analysis Set as a sensitivity analysis. Should the results disagree qualitatively, the ITT results will be considered the less-biased results; however, a careful examination of putative causes for the differences will be fully investigated to inform the design of subsequent research studies.

## 8.0 Participant Safety, Adverse Events, and Clinical Endpoints

All study-related adverse events occurring during the study, including those not meeting the criteria of an Unanticipated Adverse Device Effect (UADE) will be recorded on the appropriate case report form. Records of these events will be maintained and reports submitted to the FDA and IRB according to the regulatory requirements. Expected clinical adverse events and non-significant (not serious) clinical adverse events will not be reported. Expected clinical adverse events and anticipated adverse device effects are those listed in Section 2.4.

### 8.1 *Institutional Review Boards*

Before initiating this study, the protocol, informed consent forms, recruitment materials, and other relevant information will be reviewed and approved by each participating site’s

institutional review boards (IRB). Any amendments to the protocol must be approved by each institution's IRB before they are implemented.

## **8.2 *Definitions***

### **8.2.1 *Unanticipated Adverse Device Effect (UADE)***

A UADE is any serious adverse effect on health or safety or any life-threatening problem or death caused by, or associated with, a device if that effect, problem, or death was not previously identified in nature, severity, or degree of incidence in the investigational plan or IDE application (including a supplementary plan or application), or any other unanticipated serious problem associated with a device that relates to the rights, safety, or welfare of subjects.

### **8.2.2 *Study-Related Adverse Effect (Event)***

Any untoward medical occurrence in a subject involved in a clinical study of an investigational device that has a causal relationship with the device or, if applicable, other study related treatment(s).

### **8.2.3 *General Physical Examination Findings***

At screening, any clinically significant abnormality should be recorded as a preexisting condition. At the end of the study, any new clinically significant findings/abnormalities that meet the definition of a study-related adverse event must also be recorded and documented as an adverse event.

### **8.2.4 *Hospitalization, Prolonged Hospitalization, or Surgery***

Any adverse event that results in hospitalization or prolonged hospitalization should be documented and reported as an unanticipated adverse device effect unless specifically instructed otherwise in this protocol. Any condition responsible for surgery should be documented as an adverse event if the condition meets the criteria for a study-related adverse event.

Neither the condition, hospitalization, prolonged hospitalization, nor surgery are reported as an adverse event in the following circumstances:

- Hospitalization or prolonged hospitalization for diagnostic or elective surgical procedures for a preexisting condition. Surgery should **not** be reported as an outcome of an adverse event if the purpose of the surgery was elective or diagnostic and the outcome was uneventful.

- Hospitalization or prolonged hospitalization required to allow efficacy measurement for the study.
- Hospitalization or prolonged hospitalization for therapy of the target disease of the study, unless it is a worsening or increase in frequency of hospital admissions as judged by the site PI.

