#### **2.4.4 Expected Clinical Events**

Expected clinic events include those related to heart failure. Examples include:

- ER visits
- Hospitalizations
- Death

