#### **4.6.4 Primary Safety Endpoints**

- All cases of skin irritation requiring prescription treatment and/or withdrawal from the study will be documented
- All Serious Adverse Device Events (SADE) and Unexpected Adverse Device Events (UADE) will be documented and reported according to IRB and federal guidelines.

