### **8.5     *Recording of Adverse Events***

At each contact with the subject, the investigator must seek information on study-related adverse events by specific questioning and, as appropriate, by examination. Study subjects will be routinely questioned about study-related adverse effects at study visits. Information on all study-related adverse events should be recorded immediately in the source document, and also in the appropriate adverse event section of the case report form (CRF). All clearly related signs, symptoms, and abnormal diagnostic, laboratory, or procedure results should be recorded in the source document.

All study-related adverse events occurring during the study period must be recorded. All observed or volunteered adverse effects (serious or non-serious) and abnormal test findings, regardless of the treatment group if applicable or suspected causal relationship to the investigational device or if applicable other study treatment or diagnostic product(s) will be recorded in the subjects' case history. For all adverse effects sufficient information will be pursued and/or obtained as to permit: an adequate determination of the outcome; an assessment of the causal relationship between the adverse effect and the

investigational device; or if applicable other study treatment or diagnostic product. The clinical course of each study-related event should be followed until resolution, stabilization, or until it has been ultimately determined that the study treatment or participation is not the probable cause. Serious adverse events that are still ongoing at the end of the study period must be followed up to determine the final outcome. Any serious adverse event that occurs after the study period and is considered to be at least possibly related to the study treatment or study participation should be recorded and reported immediately.

The Adverse Event CRF shall include the following information:

- Subject Study Number/Identifier
- Device information (BG kit and serial number)
- Date of event onset
- Date investigator became aware of event
- Description of the event
- Description of treatment the subject received as a result of the event
- Indication if study treatment was discontinued or if investigational device was removed
- Subject's current status or if the event was resolved
- Date of resolution
- Investigator assessment of the event and justification for determination

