- Investigator assessment of causality and relationship to device and study treatment

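### Section 8.2.4 makes an adverse event with hospitalization a UADE by default, without the device-association and not-previously-identified tests that Section 8.2.1 requires

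*Combined protocol and SAP*

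**What the plan says.** All references are to the combined protocol and SAP.

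- **8.2.4, default rule:** "Any adverse event that results in hospitalization or prolonged hospitalization should be documented and reported as an unanticipated adverse device effect unless specifically instructed otherwise". The next sentence, on surgery, carries a condition: "Any condition responsible for surgery should be documented as an adverse event if the condition meets the criteria for a study-related adverse event". Three exemptions follow: elective or diagnostic stays for a preexisting condition, stays needed for efficacy measurement, and stays to treat the target disease. The last is lost if the site PI judges that the disease is worse or admissions more frequent.
- **8.2.1, definition:** a UADE must be serious, a threat to life or fatal, and it must be "caused by, or associated with, a device if that effect, problem, or death was not previously identified in nature, severity, or degree of incidence". What counts as already identified is set by the plan or the IDE application. A second limb covers other serious problems, again only if unanticipated and associated with a device.
- **4.6.4, endpoint:** "All Serious Adverse Device Events (SADE) and Unexpected Adverse Device Events (UADE) will be documented and reported according to IRB and federal guidelines". The abbreviation is expanded slightly differently here than in 8.2.1.
- **8.0 and 2.4.4, expected events:** "Expected clinical adverse events and non-significant (not serious) clinical adverse events will not be reported". Section 2.4.4 adds: "Expected clinic events include those related to heart failure".
- **8.4:** hospital readmissions are recorded as clinical endpoints and sent to the Project Coordinator.
- **8.5:** adverse effects go into the case history "regardless of the treatment group if applicable or suspected causal relationship to the investigational device". The adverse event form asks for the device kit and serial number and for "Investigator assessment of causality and relationship to device and study treatment".
- **8.6 and 8.7:** the device manufacturer reviews documented UADEs. It files an FDA form only for effects determined to be UADEs.

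**The concern.** Hospitalization is evidence that an event is serious. It says nothing about whether the device was involved or whether the event was foreseen. A rule that moves from hospitalization straight to UADE therefore skips two of the three elements of the protocol's own definition.

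At stake is what a reported UADE means. A site working from 8.2.4 and a site working from 8.2.1 could classify the same admission differently, and the resulting count belongs to a primary safety endpoint. In a recently hospitalized heart failure population, admissions for other illnesses are to be expected, so the ambiguity is likely to arise in practice.

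**Working it through.** **Step 1. The two rules side by side.**

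| Test | 8.2.1 | 8.2.4 default |
|---|---|---|
| Serious | required | met by the hospitalization |
| Caused by or associated with the device | required | not stated |
| Not previously identified / unanticipated | required | not stated |

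**Step 2. Do the exemptions close the gap?** Take an unplanned admission for a new pneumonia or a fall.

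- The three exemptions in 8.2.4 do not apply: the stay is not elective or diagnostic, not for efficacy measurement, and not for HF.
- Sections 8.0 and 2.4.4 leave expected events unreported, but the only category that 2.4.4 names is HF-related.
- Section 8.2.6 may remove a worsening preexisting condition that is not study-related. It does not reach a new illness.
- Section 8.4 gives every readmission a clinical-endpoint route, but does not say that the event is then not a UADE.

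None of these clearly removes the event. None depends on arm either, and patients in the standard care arm (4.3) wear no study device.

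**Step 3. Does reading adverse event as study-related repair it?** Section 8.2.2 would then supply a causal test. It has no test of whether the event was already identified, so the third row of the table stays empty.

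**Step 4. Scale.** The point rests on no figure in the plan. The planning rates in 7.1 serve only to show scale. The figure of 152 per group reproduces with pooled variance and no continuity correction:

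n = [1.960 × √(2 × 0.1875 × 0.8125) + 0.8416 × √(0.25 × 0.75 + 0.125 × 0.875)]² / 0.125² = 151.9, rounded up to 152.

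Under the 4:1 allocation in 4.2:

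- Tele-HC: 304 × 0.8 = 243.2 patients; × 0.125 = 30.4 readmitted.
- Control: 304 × 0.2 = 60.8 patients; × 0.25 = 15.2 readmitted.

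The non-HF share of readmitted patients is not given. It is assumed here, equal in both arms:

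| Assumed non-HF share | Tele-HC | Control | Total |
|---|---|---|---|
| 10% | 3.0 | 1.5 | 4.6 |
| 33% | 10.1 | 5.1 | 15.2 |
| 50% | 15.2 | 7.6 | 22.8 |
| 75% | 22.8 | 11.4 | 34.2 |
| 100% | 30.4 | 15.2 | 45.6 |

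With the equal groups of 152 in 7.1, 152 × 0.125 = 19 and 152 × 0.25 = 38 are readmitted. The totals then run from 5.7 (10%) to 57 (100%).

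These are patients, not admissions. Elective stays and cases removed by 8.2.6 have not been taken off, so each row is an upper figure for its assumed share.

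**Step 5. Can the preliminary data in 2.3 fix the share?** No.

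- In the 142-patient cohort, 142 × 0.042 ≈ 6 all-cause and 142 × 0.028 ≈ 4 cardiac readmissions leave 2 of 6 non-cardiac (exact 95% interval 4% to 78%). That cohort mixes HF and AMI patients at 30 days, and non-cardiac is not the same as non-HF.
- The 30-patient study had 6% readmitted (30 × 0.06 = 1.8, about 2 patients) and none for HF, a share of 100% on a very small number.

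**The case against.** The best defence is that the safety section is built on study-relatedness. Section 8.0 puts study-related events on the form, 8.2.2 defines them by causation, and 8.2.3, 8.2.6 and the surgery sentence of 8.2.4 all apply that condition. On this view 8.2.4 is merely loose. The exemption for HF stays still has work to do, because 2.4.2 lists delayed response and false reassurance as risks, so an HF stay could be argued to be study-related. The wording in 8.5 about treatment group and causal relationship governs what enters the case history; it is not a UADE rule. The form's request for a device serial number also sits badly with control-arm UADEs.

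This is a plausible reading, and it weakens any firm claim that unrelated control admissions will be filed as UADEs. It does not remove the conflict: the not-previously-identified test is still absent, and the study-related condition is written for surgery but not for hospitalization in the adjoining sentence.

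A second defence is that the 8.6 process opens with a study-related event, so unrelated admissions never enter it. That holds only in part, because 8.6 also commits the manufacturer to review documented UADEs, and 8.2.4 tells sites to document these admissions as such.

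Third, Section 8.8 (Reporting Process) and the Data and Safety Monitoring Plan in Appendix 15.4 could not be seen and might settle the routing. That limit stands.

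**Conclusion.** The point holds as a defect in a stated rule: 8.2.4 directs a UADE classification that 8.2.1 would not support. An unplanned non-HF admission in either arm could be filed as a UADE on the literal text. The size cannot be determined from the documents. About 5 to 46 patients is an illustration that rests on the planning rates, 4:1 allocation and an assumed non-HF share of 10% to 100%.

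A reader might infer more, and the documents do not support it:

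- **A distorted comparison between arms, or a masked device effect.** Section 7 plans no UADE rate, test or comparison, and 4.6.4 is a commitment to document and report.
- **A flood of unrelated FDA reports.** Section 8.7 forwards only effects determined to be UADEs.
- **Loss of information.** The form records relation to the device, so misfiled events can be re-sorted.
- **A threat to efficacy.** Readmissions are captured separately for the primary endpoint.

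What remains is inconsistent safety classification, and no visible statement of whether 4.6.4 counts events as filed or after review. It is a modest point, worth correcting because the correction is cheap.

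**What to change.** In 8.2.4, replace the default with three statements:

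1. An adverse event resulting in hospitalization or a prolonged stay is recorded as serious unless exempt under 8.0, 2.4.4 or the listed exceptions.
2. Readmissions are also recorded as clinical endpoints under 8.4.
3. The event is a UADE only if it also meets 8.2.1.

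In 4.6.4, state that the UADEs counted are those meeting 8.2.1 after the 8.6 review, and use the same expansion of the abbreviation as 8.2.1.

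The cost is a wording amendment, a note to sites, and re-review of any event already filed as a UADE only because of hospitalization. No new visits, data items or patients are needed.

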### **8.2.5 Post-study Adverse Event**

All unresolved study-related adverse events should be followed by the investigator until the events are resolved, the subject is lost to follow-up, or the adverse event is otherwise explained. At the last scheduled visit, the local investigator should instruct each subject to report any subsequent event(s) that the subject, or the subject's personal physician, believes might reasonably be related to participation in this study. The local investigator should notify the study regulatory sponsor of any death or adverse event occurring at any time after a subject has discontinued or terminated study participation that may reasonably be related to this study. The sponsor should also be notified if the local investigator should become aware of the development of problems, cancer, or of a congenital anomaly in a subsequently conceived offspring of a subject that has participated in this study.

### **8.2.6 Preexisting Condition**

A preexisting condition is one that is present at the start of the study. A preexisting condition should be recorded as an adverse event if the frequency, intensity, or the character of the condition worsens during the study period and the adverse event is considered to be study related.

### **8.2.7 Unanticipated Problems Involving Risk to Subjects or Others (UPIRTSO)**

Any unanticipated problem or adverse event that meets all of the following three criteria:

- Serious: Serious problems or events that results in significant harm, (which may be physical, psychological, financial, social, economic, or legal) or increased risk for the subject or others (including individuals who are not research subjects). These include: (1) death; (2) life threatening adverse experience; (3) hospitalization - inpatient, new, or prolonged; (4) disability/incapacity - persistent or significant; (5) birth defect/anomaly; (6) breach of confidentiality and (7) other problems, events, or new information (i.e. publications, DSMB reports, interim findings, product labeling change) that in the opinion of the local investigator may adversely affect the rights, safety, or welfare of the subjects or others, or substantially compromise the research data, **AND**

- Unanticipated: (i.e. unexpected) problems or events are those that are not already described as potential risks in the protocol, consent document, not listed in the Investigator's Brochure, or not part of an underlying disease. A problem or event is "unanticipated" when it was unforeseeable at the time of its occurrence. A problem or event is "unanticipated" when it occurs at an increased frequency or at an increased severity than expected, **AND**
- Related: A problem or event is "related" if it is possibly related to the research procedures.

### **8.3     *Clinical Endpoints/Adverse Event Reporting Period***

For this study, the study treatment follow-up period is defined as 60 days following the administration of study treatment. The study period during which clinical endpoints and adverse events must be reported is defined as the period from the initiation of any study procedures to the end of the study treatment follow-up.

### **8.4     *Recording of Clinical Endpoints***

Information on all clinical endpoints will be recorded in the source documentation and in the applicable CRF.

When a hospital readmission occurs, the site coordinator will record the information in the source documentation and in the applicable CRF and will forward all relevant de-identified medical information to the Project Coordinator for review.

### **8.5     *Recording of Adverse Events***

At each contact with the subject, the investigator must seek information on study-related adverse events by specific questioning and, as appropriate, by examination. Study subjects will be routinely questioned about study-related adverse effects at study visits. Information on all study-related adverse events should be recorded immediately in the source document, and also in the appropriate adverse event section of the case report form (CRF). All clearly related signs, symptoms, and abnormal diagnostic, laboratory, or procedure results should be recorded in the source document.

All study-related adverse events occurring during the study period must be recorded. All observed or volunteered adverse effects (serious or non-serious) and abnormal test findings, regardless of the treatment group if applicable or suspected causal relationship to the investigational device or if applicable other study treatment or diagnostic product(s) will be recorded in the subjects' case history. For all adverse effects sufficient information will be pursued and/or obtained as to permit: an adequate determination of the outcome; an assessment of the causal relationship between the adverse effect and the

investigational device; or if applicable other study treatment or diagnostic product. The clinical course of each study-related event should be followed until resolution, stabilization, or until it has been ultimately determined that the study treatment or participation is not the probable cause. Serious adverse events that are still ongoing at the end of the study period must be followed up to determine the final outcome. Any serious adverse event that occurs after the study period and is considered to be at least possibly related to the study treatment or study participation should be recorded and reported immediately.

The Adverse Event CRF shall include the following information:

- Subject Study Number/Identifier
- Device information (BG kit and serial number)
- Date of event onset
- Date investigator became aware of event
- Description of the event
- Description of treatment the subject received as a result of the event
- Indication if study treatment was discontinued or if investigational device was removed
- Subject's current status or if the event was resolved
- Date of resolution
- Investigator assessment of the event and justification for determination
- Investigator assessment of causality and relationship to device and study treatment

## **8.6 *Preventice Reporting of Unanticipated Adverse Device Effects and Unanticipated Problems***

When a study-related adverse event has been identified, the study team will take appropriate action necessary to protect the study participant and then complete the Study Adverse Event CRF. Preventice will evaluate the event and determine the necessary follow-up and reporting required as it relates to device related events. Those that may necessitate reporting but are not device related will be addressed by Mayo Clinic.

Preventice will promptly review documented Unanticipated Adverse Device Effects and as necessary shall report the results of such evaluation to the FDA within 10 working days of initial notice of the effect. Thereafter, Preventice will submit such additional reports concerning the effect as requested.

#### ***8.7 Preventice Reporting, Notifying the FDA***

Preventice will report to the FDA all unanticipated adverse device effects according to the required reporting timelines, formats and regulations.

Preventice will submit a completed FDA Form 3500A to the FDA's Center for Devices and Radiological Health for any observed or reported adverse effect that is determined to be an unanticipated adverse device effect. A copy of this completed form will be provided to the DSMB and all participating sub-investigators.

The completed FDA Form 3500A will be submitted to the FDA as soon as possible and, in no event, later than 10 working days after Preventice first receives notice of the adverse effect.

If the results of Preventice's follow-up evaluation shows that an adverse effect that was initially determined to not constitute an unanticipated adverse device effect does, in fact, meet the requirements for reporting; Preventice will submit a completed FDA Form 3500A as soon as possible, but in no event later than 10 working days, after the determination was made.

For each submitted FDA Form 3500A, Preventice will identify all previously submitted reports that addressed a similar adverse effect experience and will provide an analysis of the significance of newly reported adverse effect in light of any previous, similar report(s).

Subsequent to the initial submission of a completed FDA Form 3500A, Preventice will submit additional information concerning the reported adverse effect as requested by the FDA.

